6.6.5 Interruption or Discontinuation of Study Drug

The term “interruption” refers to a patient stopping all study drug during the course of the study, but then re-starting it at a later time in the study. If treatment has to be interrupted for more than 14 days for any reason other than toxicities suspected to be related to RAD001, the patient will be discontinued from the study. If treatment has to be interrupted for more than 21 days due to suspected study drug-related toxicity, the patient will be discontinued from the study.

Tumor evaluations will continue until the start of new anticancer therapies. The term “discontinuation” refers to a patient’s premature withdrawal from the study treatment. In accordance with the current revision of the Declaration of Helsinki and current US Food and Drug law, a patient has the right to withdraw from the study at any time for any reason without prejudice to his/her future medical care by the physician or at the institution.

The reason for discontinuation from treatment will be recorded on the appropriate CRF page. The patient may discontinue participation in the study for any of the following reasons:

1. Adverse event(s);
2. Abnormal laboratory value(s);
3. Abnormal test procedure result(s);
4. Disease progression;
5. Protocol violation;

6. Patient withdrew consent;
7. Lost to follow-up;
8. Administrative problems;
9. Death.

If a patient has discontinued the study due to an unacceptable adverse drug reaction or an abnormal laboratory value, he/she should not have withdrawal of consent recorded as the reason for discontinuation. Instead, the reason for discontinuation must be recorded as due to adverse drug reaction or an abnormal laboratory value.

6.6.6 Patient Withdrawal

6.6.6.1 End of Treatment

All cancer medications/therapies given to a patient ≤ 4 weeks after the last dose of study treatment must be recorded on the CRF.

Patients who discontinue the study regardless of the reason must have end-of-study treatment evaluations (see Table 9) on the day of study drug discontinuation or within 2 weeks of study drug discontinuation. The investigator or his/her designee will proceed as follows:

- Notify clinical team immediately of patient discontinuation;
- Complete the end of study assessments and complete the End-of-Treatment CRF page indicating the date and reason for stopping the study drug. Additional details are provided in Table 9;
- All patients will have a follow-up visit 28 days after the last dose of the study drug. During this visit, AE and SAE information will be collected and recorded on the appropriate CRF pages. If the patient is unable to return to the clinic, the investigator or his/her designee will contact the patient or caregiver to collect this information;
- All patients who are discontinued from the study drug for any reason (i.e., documented disease progression by the investigator, an AE or SAE, administrative reasons, etc.) will continue to have tumor assessments at 12-week intervals until the initiation of new anticancer therapy. This information will be recorded on the appropriate CRF pages;
- If patients refuse to return to the clinic for follow-up assessments or are unable to do so, the investigator or his/her designee will make every effort to contact the patient, a close relative, or caretaker by telephone to collect survival information. The investigator or his/her designee should show “due diligence” by documenting on the source documents steps taken to contact the patient, i.e., dates of telephone calls, registered letters, etc.

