- ^a Pulmonary function tests (including spirometry, diffusion capacity of carbon monoxide, and room air O₂ saturation at rest) will be performed at screening per investigator discretion, and at the end of the study (≤2 weeks) and as medically necessary if there is evidence of non-infectious pneumonitis. A bronchoscopy with a biopsy and/or bronchoalveolar lavage will be performed when medically necessary for decisions regarding patient care. The results will be recorded on the appropriate CRF page.
 - ^o Record all medications given ≤30 days prior to study entry on the Concomitant Medications/Significant Non-Drug Therapies Prior to the Start of the Study CRF page. After the start of the study, concomitant medications must be recorded on the Concomitant Medications/Significant Non-Drug Therapies CRF page.
 - ^p All adverse events (AEs) occurring after the start of the study, even if the event is not considered to be related to the study drug, must be documented on the Adverse Event CRF page.
 - ^q Information on all target tumor and non-target lesions will be collected at screening. Subsequently, radiological assessments (to follow the target and non-target lesions identified at baseline) will be performed at 8 weeks (±1 week). In the absence of progressive disease, assessments will continue every 12 weeks (±1 week) until the start of new anticancer therapy and at the End-of-Study Visit (within 1 week of stopping treatment) or until death. Observation of tumor response (partial or complete response) warrants a confirmation no sooner than 4 weeks. The same type of scan (CT or MRI) used at screening must be used for all subsequent follow-up assessments.
 - ^r RAD001 10 mg daily dosing will begin on Day 1 of Cycle 1. Treatment with the study drug will continue until disease progression, unacceptable toxicity, withdrawal of consent, death, etc.
 - ^s Patients who discontinue the study drug will have end-of-study evaluations performed on that day or within 2 weeks of discontinuation of the study drug.
 - ^t All patients will have a follow-up visit 28 days after the last dose of RAD001. During this visit, AE and serious adverse event information occurring since the last dose of study drug will be collected and recorded on the appropriate CRF pages. All patients who are discontinued from the study drug for any reason will continue to have tumor assessments until the start of any new anticancer therapy.

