7.6.1 Adverse Events

An AE, for the purposes of this protocol, is the appearance of (or worsening of any pre-existing) undesirable sign(s), symptom(s), or medical condition(s) occurring after signing the informed consent, even if the event is not considered to be related to the study drug (study drug refers to the drug under evaluation [RAD001], and study treatment also refers to RAD001).

Adverse events will be assessed according to the CTCAE, version 3.0. If CTCAE grading does not exist for a particular AE, the severity of mild, moderate, severe, and life-threatening, or grades 1 to 4, will be used. The CTCAE grade 5 (death) will not be used in this study; rather, this information will be collected on the End of Treatment or Survival Information CRF page. All AEs will be coded by System Organ Class (SOC) and preferred term using the Medical Dictionary for Regulatory Activities (MedDRA), latest version.

Adverse event monitoring should be continued for at least 4 weeks following the last dose of study treatment. Adverse events (but not SAEs) occurring before starting study treatment, but after signing the informed consent form, are recorded on the Medical History/Current Medical Conditions CRF pages. Abnormal laboratory values or test results constitute an AE only if they induce clinical signs or symptoms, are considered clinically significant, or require therapy (e.g., any hematological abnormality that requires transfusion or cytokine treatment); and should be recorded on the Adverse Events CRF page under the signs, symptoms, or diagnosis associated with them. In addition, isolated abnormal laboratory values that are considered clinically significant (e.g., cause study discontinuation or constitutes in and of itself a SAE) should be recorded on the Adverse Events CRF page. Serious AEs occurring after signing the Informed Consent are recorded on the Adverse Event CRF page.

The occurrence of AEs should be sought by non-directive questioning of the patient at each visit during the study. Adverse events may also be detected when they are volunteered by the patient during or between visits or through physical examination, laboratory test, or other assessments.

As far as possible, each AE should be evaluated to determine:

1. The severity grade (CTCAE grades 1 to 4);
2. Its relationship to study drug (suspected/not suspected);
3. Its duration (start and end dates or if continuing at final exam);

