3.1 Assessments

Upon provision of written, informed consent patients will be given a unique 9 digit patient number. This will be a combination of their 4 digit center number and 5 digit subject number.

The patient will be assessed for their eligibility to take part in the study (i.e. receive study medication) using the inclusion and exclusion criteria stated in the protocol (Sections 5.1 and 5.2). If the patient fails to start on treatment for any reason, this reason will be entered on the Screening Log. No data for screen failures will be entered into the clinical database.

Patients who are eligible for treatment will be dispensed their study medication on completion of their baseline visit. Patients should present to the clinic on Day 1 and Day 15 of treatment Cycles 1, 2, and 3 and Day 1 of each subsequent treatment cycle to complete the assessments detailed in Table 6 of the protocol, until completion of treatment which will occur when the patient experiences disease progression, unacceptable toxicity, death or discontinues from the study for any other reason. An end of study treatment assessment should then be performed. All patients will have a follow-up visit 28 days after the last dose of the study drug to follow for adverse events (AEs) and serious adverse events (SAEs) that may have occurred after discontinuation from the study.

Tumor response will be assessed at 8 weeks (+/- 1 week), and every 12 weeks (+/- 1 week) thereafter until determination of disease progression and at the end of the study.

Patients who discontinue treatment, or are withdrawn from treatment by the investigator, for any reason, should complete an early discontinuation assessment. All patients who discontinue treatment will continue to have tumor assessments at 12-week intervals until the initiation of new cancer therapy.

The efficacy assessments for this study will be the assessment of tumor response/progression and survival status. Tumor response/progression assessments should be performed by a Computerized Tomography (CT) or Magnetic Resonance Imaging (MRI) scan. The same imaging modality used at screening must be used for all subsequent follow-up assessments.

Safety assessments will consist of evaluating AEs and SAEs, laboratory parameters including hematology, chemistry, vital signs and documentation of all concomitant medications and/or therapies. The Karnofsky Performance Status score will also be recorded.

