7. STATISTICAL ANALYSIS METHODS

7.1 General Principles

The number of patients in the population of interest will be presented on each table, shown as N=XXX. For data summarized by visit, the N will be the number of patients in the population of interest still present in the study at that visit. See Section 7.3 on Patient Disposition for a full definition.

Data from unscheduled visits will be listed only, except for the End of Treatment row in safety tables if the unscheduled visit is the patient's last on-treatment record.

No visit windowing will be applied for this study. However, it will be checked when summarizing any data that are collected by visit that on-treatment assessments did actually take place prior to the end of treatment date. Should an on-treatment assessment be performed later than the date of last treatment, the data will be listed but will not be included in the summary tables. The timing of off-treatment data will be checked again prior to database lock as data collected within 30 days of end of treatment may be considered valid for use in summary tables in which case this definition will be updated to allow for these cases.

It should be noted this rule does not cover adverse event data which have a separate definition of on-treatment.

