7.5 Demographic and Baseline Characteristics

Demographic data including date of birth, sex, race and ethnicity will be collected at Screening Visit 1a. Age will be derived as the age in years at Screening Visit 1a. Age, sex, race, ethnicity, height, weight, BMI and Karnofsky Performance Status will be summarized for the ITT population. In the event of a difference between the safety and ITT populations, this summary of demographic data will be repeated for the safety population.

The date of informed consent, any failed inclusion or exclusion criteria and the source of subject referral will be listed only.

Relevant medical history and current medical conditions are collected at Screening Visit 1a. The number of patients with at least one relevant medical history or current medical condition and at least one active problem will be presented and a summary will also be provided of the medical history by body system and preferred term. These summaries will be performed on the ITT population.

A pregnancy test is performed at Screening Visit 1a and Baseline Visit 1b and the data collected will be listed only. If any unscheduled pregnancy tests are performed during the treatment or follow-up periods of the study these data will also be listed.

Each patient's prior antineoplastic therapy is recorded at Screening Visit 1a. The number of patients taking each therapy type overall and by setting will be presented along with the total number of separate courses of therapy. Each separate record entered on the CRF will be counted as a separate course of therapy. For each therapy type/setting combination the overall best response per patient will be determined as either Complete Response (best), Partial Response, Stable Disease, Complete Response (unconfirmed), Unknown, Not Applicable or Progressive Disease (worst). The total duration of time per therapy type/setting will be calculated for each patient based on the CRF data. It is expected the duration will be calculated in months and should take into account any overlap in dates recorded on the CRF. See Section 7.2.2 regarding the handling of partial dates. Summaries of prior antineoplastic therapy will be performed on the ITT population, and in the event of a difference between the safety and ITT populations will be repeated for the safety population.

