8.1 Adverse Events

All AEs will be coded using the Medical Dictionary for Regulatory Activities (MedDRA®) Version 12.1 to provide the system organ class (SOC) and preferred term for each AE.

An adverse event will be defined as treatment emergent if it begins on or after the first day of dosing with study medication and no later than 30 days after the last dose of study medication. It is expected that adverse event monitoring will continue for at least 4 weeks after the last dose of study medication but new events occurring after the end of the treatment period will not be recorded on the CRF (unless they are serious or lead to death).

Since adverse events occurring prior to start of study or between signing informed consent and start of study medication should be considered as medical history, it is anticipated that all adverse events will be treatment emergent adverse events. However, in the event of any non-treatment emergent adverse events occurring, these will be indicated on the adverse event listings. Non-treatment emergent adverse events are defined as events that begin prior to the first day of dosing. If these events are Serious Adverse Events (SAEs) then they will also be summarized.

The number of patients experiencing each of the following will be summarized:

- At least one treatment emergent adverse event (TEAE)
- At least one SAE
- At least one SAE with a suspected relationship to study medication
- At least one adverse TEAE event leading to death
- At least one TEAE leading to modification of study medication
- At least one TEAE leading to permanent discontinuation of study medication
- At least one severe TEAE
- At least one TEAE with a suspected relationship to study medication

Serious adverse events will be indicated on the CRF, as will adverse events leading to modification or permanent discontinuation of study medication. The addition of non-drug therapy will not be classed as a modification of study medication.

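### SAP 8.1 says new non-serious adverse events after treatment will not be recorded, against the protocol's recording rule and the SAP's own 30-day treatment-emergent window

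*Protocol*

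**What the plan says.** The protocol is consistent about what is recorded after the last dose.

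- Section 6.6.6.1, on the visit 28 days after the last dose: "During this visit, AE and SAE information will be collected and recorded on the appropriate CRF pages".
- Table 9, footnote t, on the same visit: "AE and serious adverse event information occurring since the last dose of study drug will be collected and recorded on the appropriate CRF pages".
- Table 9, footnote p, requires every adverse event after study start, related or not, on the Adverse Event CRF page. The adverse event row of that table is marked in the follow-up column.
- Section 7.6.1: "Adverse event monitoring should be continued for at least 4 weeks following the last dose of study treatment".

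SAP 3.1 repeats the visit, "to follow for adverse events (AEs) and serious adverse events (SAEs) that may have occurred after discontinuation from the study".

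SAP 8.1 makes two statements. An event is treatment-emergent if it starts on or after the first dosing day and "no later than 30 days after the last dose of study medication". Monitoring is expected to go on for at least 4 weeks after the last dose. In the same sentence, however, "new events occurring after the end of the treatment period will not be recorded on the CRF"; only serious and fatal events are excepted.

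**The concern.** The two statements in SAP 8.1 do not fit together, and the second does not fit the protocol. A window that runs to 30 days after the last dose is meant to hold all adverse events with onset in it. If new non-serious events stop being recorded when dosing stops, the post-dose part of the window can hold only serious or fatal ones. A reader of the treatment-emergent tables would assume complete collection throughout.

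Protocol 10.5.2 rests the safety assessment mainly on adverse event frequency, and this is a single-arm study, so incomplete counts are not offset by a control group with the same gap. SAP 8.3 takes the End of Treatment laboratory value from up to 30 days after the last dose, so laboratory and adverse event tables could cover different periods. The shells for Tables 14.5-1.1 and 14.5-2.1 carry no footnote on post-dose collection.

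**Working it through.** The point is mainly a comparison of texts, with no stated figure to reproduce.

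**Step 1: the rules side by side, for a new non-serious event starting after the last dose**

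| Source | Recorded on the CRF? | Treatment-emergent? |
|---|---|---|
| Protocol 6.6.6.1; Table 9 footnotes p and t | Yes | Not defined there |
| SAP 8.1, recording clause (end of treatment period read as end of dosing) | No | – |
| SAP 8.1, definition | – | Yes, to day 30 |

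**Step 2: what the treatment period means.** SAP 8.1 does not define it. Three things favour the end of dosing. The clause is set by a *but* against monitoring after the last dose. SAP 7.5 speaks of tests "during the treatment or follow-up periods of the study", so the SAP treats these as separate periods. SAP 8.6 measures treatment duration from first to last dose.

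**Step 3: how much of the window is post-dose.** For a patient dosed for D days the share is 30/(D + 30), with a month of 365.25/12 = 30.44 days.

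- D = 56 days (first scheduled scan, 8 weeks): 30/86 = 34.9%.
- D = 4.0 months = 121.8 days (RAD001 median PFS quoted in the protocol synopsis): 30/151.8 = 19.8%.
- D = 10 months = 304.4 days (time point of the sample size calculation): 30/334.4 = 9.0%.

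These are shares of calendar time, not of events.

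**Step 4: patients affected.** The documents give no rate of new non-serious events off drug. As a pure assumption, take 5%, 10% or 20% of patients with at least one:

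- N = 110 (protocol): 5.5, 11 or 22 patients.
- N = 142 (SAP 3): 7.1, 14.2 or 28.4 patients.

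One patient moves a preferred-term row by 1/110 = 0.9 or 1/142 = 0.7 percentage points.

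**Step 5: which rows can move.** The row for at least one treatment-emergent event would hardly change: in protocol Table 1, 43 of 45 patients (96%) on 10 mg daily already had a suspected event. Events starting after the last dose cannot have led to dose modification or discontinuation. The exposed rows are the preferred-term and system-organ-class counts, suspected relationship, and severe but non-serious events.

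**Step 6: the end of the window.** Scheduled collection is at day 28 and the definition runs to day 30, so 30 − 28 = 2 days lie beyond the visit under either rule.

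**The case against.** The strongest reply is that the protocol governs collection, speaks with one voice, and allows no authorized deviations (Protocol 12). The SAP clause stands in a sentence about what is expected; it forecasts CRF content and instructs no site. SAP 1.1 uses all available CRF data, treatment-emergent status depends only on onset date, and SAP 8.1 lists every captured event. A recorded post-dose event therefore enters Table 14.5-2.1 whatever the clause says. All of this stands. A reader might infer that the SAP discards these events, or that they are known to be missing. The documents support neither: data are lost only if the CRF or its completion followed the clause, and neither is visible here.

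A second reply is that the treatment period could mean the 30-day window. SAP 7.1 refers to "adverse event data which have a separate definition of on-treatment", and SAP 7.5 speaks of medications used during the treatment period and then counts those starting up to 30 days after the last dose. On that reading SAP 8.1 is coherent. The reading is possible but is the less natural one, for the reasons in Step 2, and a clause that permits both needs rewording anyway.

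Third, the post-dose share overstates the likely effect. With a 30-hour half-life (Protocol 1.2.3.1), five half-lives take 150 h = 6.25 days, so about 79% of the 30 days, (30 − 6.25)/30, follows washout. This also stands.

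Two further inferences are tempting and should not be drawn.

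- *Pneumonitis.* The end-of-treatment CT may come up to 2 weeks after stopping, so a reader might infer that grade 1 pneumonitis seen on it would be lost. But Protocol 7.6.1 makes a test result an adverse event only if it causes symptoms, is clinically significant or needs therapy. Grade 1 pneumonitis is asymptomatic and needs no specific therapy (6.1.4.3 and Table 4), so it is not automatically an adverse event.
- *Visit anchor.* The synopsis and Section 4 time the follow-up visit from the End-of-Treatment Visit, and the other sections from the last dose. That difference alters neither the treatment-emergent definition nor SAE reportability.

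**Conclusion.** The concern holds in a limited form. On its natural reading, the recording clause in SAP 8.1 is wrong: it contradicts the protocol and undercuts the SAP's own 30-day window. What follows depends on a fact outside the documents. If the CRF followed the clause, non-serious treatment-emergent counts after the last dose in Tables 14.5-1.1 and 14.5-2.1 are incomplete without disclosure. If sites followed the protocol, the tables are complete up to the 28-day visit and only the sentence needs correcting.

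The size is unknown. The patient numbers in Step 4 rest on assumed rates and only show scale. SAEs, PFS, response and OS are unaffected. The clause should be corrected because that is cheap and the main safety tables depend on it.

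**What to change.** 1. Keep the 30-day treatment-emergent definition as it is. Redefining it to end at the follow-up visit would create a new mismatch.
2. In SAP 8.1, replace the clause with the protocol rule: all new adverse events since the last dose, serious or not, are recorded on the CRF at the 28-day follow-up visit.
3. Before database lock, check by site for non-serious events with onset after the last dose. This can sit beside the pre-lock review of off-treatment data already planned in SAP 7.1. Sites are small (about 4 patients each in protocol Table 10), so read the result overall as well as by site and compare it with the CRF instructions. No such events anywhere would suggest that the clause was followed.
4. If the events were not captured, say so in a footnote to Tables 14.5-1.1 and 14.5-2.1. Show events with onset on drug separately from those with onset on days 1–30 after the last dose.

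The cost is one sentence, a small data check and possibly one extra table split. No visit or assessment is added. The rewording cannot recover events that sites did not record, so the check and the footnote do the real work.
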